03 SEP 2018

SUMMARY OF CHANGES

Document	Date of issue	Summary of change
Revised protocol 05	03 September 2018	Incorporates amendment 05
Amendment 05	03 September 2018	This amendment was written to: Include the new sample size calculation ^a
Revised protocol 04	10 February 2016	Incorporates amendment 04
Amendment 04	10 February 2016	This amendment was written to: Modify the end point “readmission” ^b Clarify the definition of initial suspicion of PE ^c
Revised protocol 03	10 February 2016	Incorporates amendment 03
Amendment 03	10 February 2016	This amendment was written to: Modify the end point “readmission” ^b Clarify the definition of initial suspicion of PE ^c
Revised protocol 02	07 November 2015	Incorporates amendment 02
Amendment 02	07 November 2015	This amendment was written to: Include breastfeeding as an exclusion criterion
Revised protocol 01	16 May 2015	Incorporates amendment 01
Amendment 01	16 May 2015	This amendment was written to: Include clinically relevant non major bleeding as a safety event ^d
Original protocol	01 September 2014	Not applicable

^aNew sample size calculation:

After the last interim analysis, the DSMB increased the expected evaluable rate from 75% to 95%. Therefore, the final sample size decreased to 746 patients (373 per arm).

^bPrimary efficacy outcome:

“Readmission for any cause” was changed by “readmission for COPD exacerbation”.

^cDefinition of initial suspicion of PE

Defined as the indication of a D-dimer testing or a multidetector computed tomography (**CT**) angiogram by the attending physician in the Emergency Department.

^dDefinition of clinically relevant non major bleeding

Any sign or symptom of hemorrhage (e.g., more bleeding than would be expected for a clinical circumstance, including bleeding found by imaging alone) that does not fit the criteria for the ISTH definition of major bleeding but does meet at least one of the following criteria: 1) requiring medical intervention by a healthcare professional; 2) leading to hospitalization or increased level of care; or 3) prompting a face to face (i.e., not just a telephone or electronic communication) evaluation.

STEERING COMMITTEE

Co-Chairmen (Principal Investigators):

[name]. Hospital Clinic, Barcelona (Spain)

[contact]

[name]. Hospital Ramón y Cajal, Madrid (Spain)

[contact]

[name]. Hospital German Trias i Pujol, Badalona (Spain)

[contact]

[name]. Hospital Virgen del Rocío, Sevilla (Spain)

[contact]

Steering Committee:

[name]. Université de Saint-Etienne (France)

[contact]

[name]. University Hospital of Brest (France)

[contact]

[name]. Leiden University Medical Center, Leiden (Netherlands)

[contact]

[name]. Hospital Universitario Araba, Vitoria (Spain)

[contact]

[name]. Barnes Jewish Hospital, St. Louis (USA)

[contact]

Writing Committee:

[name]. Hospital Ramón y Cajal, Madrid (Spain)

[name]. Brigham and Women's Hospital, Harvard Medical School, Boston (USA)

[contact]

[name]. Hospital German Trias i Pujol, Badalona (Spain)

[name]. Barnes Jewish Hospital, St. Louis (USA)

Critical Events Adjudication Committee:

[name]. Hospital Ramón y Cajal, Madrid (Spain)

[contact]

[name]. Hospital Ramón y Cajal, Madrid (Spain)

[contact]

Data Safety Monitoring Board:

[name]. Hospital Ramón y Cajal, Madrid (Spain)

[contact]

[name]. Hospital Ramón y Cajal, Madrid (Spain)

[contact]

Central Reading:

[name]. Hospital Ramón y Cajal, Madrid (Spain)

[contact]

[name]. Hospital Ramón y Cajal, Madrid (Spain)

Trial Statistician:

[name]. Hospital Ramón y Cajal, Madrid (Spain)

[contact]

Data Monitoring:

S&H Medical Science Service

TRIAL OBJECTIVES

The objectives of the trial are:

To assess the clinical effect of an active strategy for the diagnosis and treatment of pulmonary embolism (**PE**), compared to usual care, in patients with unexplained exacerbations of chronic obstructive pulmonary disease (**COPD**) who require hospital admission.

To assess the prevalence of PE in patients with unexplained exacerbations of COPD who require hospital admission.

To identify those clinical variables associated with a diagnosis of PE in patients with unexplained exacerbations of COPD who require hospital admission.

To determine the positive predictive value of D-dimer testing for the diagnosis of PE in patients with unexplained exacerbations of COPD who require hospital admission.

STUDY PLAN

	Screening: Visit 1 Day -1	Enrollment: Visit 2 Day 0	Follow-up: Visit 3 Day 7 ± 2	Follow-up: Visit 4 Day 30 ± 5	Follow-up: Visit 5 Day 90 ± 7
Medical history	X				
Demographic variables	X				
Physical examination	X		X	X	X
COPD diagnosis	X				
Inclusion and exclusion criteria	X				
Informed consent	X				
Hematology tests	X				
Biochemistry tests	X				
Coagulation tests	X				
Chest X-ray	X				
Randomization		X			
D-dimer		Intervention group			
Multidetector CT pulmonary angiogram		Intervention group			
ASSESSMENT OF:					
Recurrent VTE			X	X	X
Death			X	X	X
Bleeding ^a			X	X	X
Adverse events ^a			X	X	X
Length of hospital stay			X	X ^b	
Readmission			X	X	X

Abbreviations: COPD, chronic obstructive pulmonary disease; CT, computed tomography; VTE, venous thromboembolism.

^aSee definitions in the protocol.

^bIf hospital admission longer than 7 \pm 2 days.

ABBREVIATED PROTOCOL

Title:	Efficacy and safety of an active strategy for the diagnosis and treatment of acute pulmonary embolism (PE) in patients with unexplained exacerbations of chronic obstructive pulmonary disease (COPD): a randomized clinical trial.
Investigators:	Multicentre.
Participating sites:	Approximately 18 study centers.
Clinical phase:	III
Objectives:	
The primary objective is to assess the benefit of an active strategy for the diagnosis and treatment of PE, compared to usual care, in patients with unexplained exacerbations of COPD who require hospital admission.
 
The secondary objective is to assess the safety of an active strategy for the diagnosis and treatment of PE compared to usual care in patients with unexplained exacerbations of COPD who require hospital admission.

Methodology: Prospective, international, multicenter, randomized (1:1), open-label with blind end-point evaluation (**PROBE**), parallel-group trial.

No. de subjects: Approximately 746 patients.

Each strategy: Approximately 373 patients.

Diagnosis and main criteria for exclusion: Patients admitted to the hospital because of COPD exacerbation. COPD exacerbation is defined as any worsening of respiratory symptoms sufficiently severe to warrant an admission to the Emergency Department in a patient with known COPD. Patients with an initial clinical suspicion of PE or deep vein thrombosis (**DVT**), a diagnosis of pneumothorax, pneumonia, or lower respiratory tract infection will be excluded from the trial.

Strategies:

Intervention group: All included patients will undergo D-dimer testing. A negative plasma D-dimer value (defined as a D-dimer level below the manufacturers assay threshold) will rule out pulmonary embolism, and no further examination will be performed. For patients with a positive D-dimer value, a thoracic multidetector helical computed tomography scan will be performed.

Control group: All included patients will undergo standard clinical management of their exacerbations, as deemed appropriate by the attending physician.

Criteria for efficacy:

Primary end point

- Clinical composite endpoint of all-cause mortality or venous thromboembolism recurrence or need for COPD readmission within 90 days.

Secondary end points

- All-cause mortality within 90 days.
- Venous thromboembolic recurrence within 90 days.
- Need for COPD readmission within 90 days.
- Length of hospital stay.

Criteria for safety:

Primary end point

- Major bleeding within 90 days.

Secondary end points

- Clinically relevant non-major bleeding within 90 days.
- Serious adverse events within 90 days.

Statistical analysis: Intent-to-treat (ITT) analysis on superiority of an active strategy for the diagnosis and treatment of PE in patients with unexplained exacerbations of COPD requiring hospital admission.

Primary criteria

The primary ITT analysis on the primary end points will be carried out by a two-sided chi-square test on proportions. In addition, the 95% confidence interval on the relative risks will be presented.

Secondary efficacy criteria

The secondary ITT analysis on the secondary efficacy end points will be carried out by a two-sided chi-square test on proportions. In addition, the 95% confidence interval on the relative risks will be presented. The survival status during 90 days follow-up will be analyzed by showing Kaplan-Meier curves, and management differences will be compared by means of log-rank test.

Secondary safety analysis

Safety end points will be tabulated by management group. All (dichotomized) end points will be analyzed by chi-square test on proportions, and the 95% confidence interval on the relative risks will be presented. In addition, continuous safety monitoring will be done by the Data and Safety Monitoring Board.

Interim analysis

Interim analysis will be made by the Data Center after recruitment of 50% of the total number of patients. These analyses will be made in order to allow sample size reassessment or early stop of the trial for efficacy or futility.

TABLE OF CONTENTS	Page
ABBREVIATIONS	15
1. BACKGROUND	16
1.1 Study justification	16
1.2 Hypothesis	17
1.3 Objectives	17
2. METHODOLOGY	20
2.1 Design	20
2.2 Setting	20
2.3 Study subjects	21
2.4 Randomization	22
2.5 Study procedures	22
2.6 Criteria for termination of the trial	23
2.7 Definition of study end points	23
2.8 Surveillance and follow-up	28

1. BACKGROUND

1.1 Study justification

Chronic obstructive pulmonary disease (**COPD**) is a leading cause of morbidity and mortality worldwide and represents a huge economic burden for the healthcare system (1-3). COPD patients may suffer from exacerbations, defined as acute worsening of respiratory symptoms that results in additional therapy (4, 5). COPD exacerbations are independent predictors of mortality in COPD and also drive disease progression, with approximately 25% of the lung function decline attributed to exacerbations (6).

The most common triggers of exacerbations are infections and air pollution, but noninfectious factors were thought to cause approximately 20% of acute exacerbations of COPD in a hospital study (7). In addition, other frequent clinical conditions may mimic the symptoms of COPD exacerbations, including congestive heart failure, pneumonia, pneumothorax, pleural effusion and pulmonary embolism (**PE**) (8).

The exact prevalence of PE in unexplained exacerbations of COPD is unclear based on the current data. Over the past decade, several studies have reported the prevalence of venous thromboembolism (**VTE**) in COPD, primarily from hospitalized patients (9-12). However, due to the heterogeneities in race, sample size, study design, research setting, and enrollment criteria, there were remarkable differences in reported data among these studies. Tillie-Leblond et al evaluated PE in a series of 197 consecutive patients with COPD and exacerbation of unknown origin, and found that the frequency of PE was 25% (13). However, that study was performed in a highly selected subgroup of patients. Rutschmann et al. showed that the prevalence of PE and deep vein thrombosis (**DVT**) in patients who were admitted to Emergency Department and with acute exacerbations of moderate-to-severe COPD was only 3.3% and 2.2%, respectively (14). In fact, a recent meta-analysis found a lower

prevalence of PE of 16% in exacerbations of compared with previous studies (15).

In patients with clinical suspicion of PE, there are some data suggesting that some PE diagnoses are less severe, and these patients might not benefit from anticoagulation therapy (16). For instance, in the PIOPED study (17), the prevalence of PE was 10% in patients with a nondiagnostic ventilation/perfusion (**V/Q**) scan and a low clinical probability of PE. Nevertheless, such patients have a low-3-month thromboembolic risk provided they have no proximal DVT. This highlights the important point that not all PEs are clinically important, especially if the main site for potential recurrence is free of clots. Particularly for patients with COPD exacerbations, some PE might be clinically unimportant, and the risk of submitting a patient with a clinically insignificant PE to anticoagulant treatment might outweigh the benefit (18).

Data from randomized controlled trials regarding the clinical effectiveness of an active search for PE in patients who have unexplained exacerbations of COPD are lacking. The objective of the Significance of Pulmonary Embolism in COPD Exacerbations (**SLICE**) is to compare health outcomes in patients with unexplained exacerbations of COPD who required hospital admission and who were randomly assigned to an active search for PE with the use of D-dimer and computerized tomography (**CT**) pulmonary angiogram, or to usual care.

1.2 Hypothesis

For patients with unexplained exacerbations of COPD who required hospital admission, an active search for PE with the use of D-dimer and, if positive, contrast-enhanced, PE-protocol, multidetector CT will improve health outcomes, compared to usual care.

1.3 Objectives

The primary objective of the SLICE trial is:

- To demonstrate the clinical benefits of an active strategy for the diagnosis and treatment of PE compared to usual care in patients with unexplained exacerbations of COPD who require hospital admission.

Secondary objectives of the SLICE trial are:

- To assess the prevalence of PE in patients with unexplained exacerbations of COPD who require hospital admission.
- To identify those clinical variables associated with a diagnosis of PE in patients with unexplained exacerbations of COPD who require hospital admission.
- To determine the positive predictive value of D-dimer testing for the diagnosis of PE in patients with unexplained exacerbations of COPD who require hospital admission.

Primary end point

Primary efficacy end point

- Clinical composite endpoint of death from any cause, non-fatal (recurrent) symptomatic VTE, or readmission for COPD exacerbation within 90 days after enrollment.

Primary safety end point

- Major bleeding within 90 days after enrollment.

Secondary end points

Secondary efficacy end points

- Death from any cause within 90 days after enrollment.
- Nonfatal (recurrent) symptomatic VTE within 90 days after enrollment.
- Need of readmission for COPD exacerbation within 90 days after enrollment.
- Length of hospital stay.

[figure not shown]
Secondary safety end points

- Clinically relevant non-major bleeding within 90 days after enrollment.
- Serious adverse events within 90 days after enrollment.

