2.7 Definition of study end points

Efficacy

The primary efficacy end point is the composite of death from any cause, non-fatal (recurrent) symptomatic VTE, or readmission for COPD exacerbation within 90 days after enrollment.

Confirmation of **(recurrent) symptomatic PE** requires symptoms of PE and a new or an extension of a previous intraluminal-filling defect in (sub)segmental or more proximal branches on PE-protocol chest CT pulmonary angiography.

Confirmation of **(recurrent) symptomatic DVT** requires symptoms of DVT and the following criteria: 1) In the absence of previous DVT investigations at baseline, a non-compressible venous segment on ultrasonography; 2) if there were previous DVT investigations at baseline, abnormal lower limb CCUS where compression had been normal; or, if previously non-compressible, a substantial increase (≥ 4 mm) in diameter of the thrombus during full compression.

Secondary efficacy end points include:

- Death from any cause within 90 days after enrollment.
- Nonfatal (recurrent) symptomatic VTE within 90 days after enrollment.
- Readmission for exacerbation of COPD within 90 days after enrollment.
- Length of hospital stay.

Safety

The primary safety end point is major bleeding within 90 days after enrollment.

Major bleeding is defined according to the guidelines of the International Society of Thrombosis and Haemostasis (20), as acute clinically overt bleeding associated with one or more among the following: a decrease in hemoglobin of 2 g/dL or more, a transfusion of two or more units of packed red blood cells, bleeding that occurs in at least one of the following critical sites (intracranial, intraspinal, intraocular, pericardial, intraarticular, intramuscular with compartment syndrome or retroperitoneal), bleeding that is fatal (defined as a bleeding event that the central independent committee adjudicate as the primary cause of death or contributing directly to death) and bleeding that necessitates surgical intervention.

Secondary safety end points include:

- Clinically relevant non-major bleeding within 90 days after enrollment.
- Serious adverse events (**SAE**) within 90 days after enrollment.

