A bleeding event is classified as a **clinically relevant non-major** bleeding event if it is overt (i.e., is symptomatic or visualized by examination) not meeting the criteria for major bleeding, requires medical attention or is associated with discomfort for the subject such as pain, or impairment of activities of daily life.

Adverse event (AE): any untoward medical occurrence in a patient or clinical investigation participants, which does not necessarily have to have a causal relationship with the study intervention. An AE can therefore be any unfavorable and unintended sign (including an abnormal laboratory finding), symptom or disease temporally associated with the use of the study medication/procedure, whether or not considered related to the study medication.

Adverse reaction (AR): all untoward and unintended responses to a medicinal product related to any dose. The phrase "responses to a medicinal product" means that a causal relationship between a study medication and an AE is at least a reasonable possibility, i.e., the relationship cannot be ruled out. All cases judged by either the reporting medically qualified professional or the sponsor as having a reasonable suspected causal relationship to the study medication/procedure qualify as adverse reactions.

Serious adverse event: an event that fulfils one or more of the following criteria:

- Fatal.
- Immediately life-threatening.
- Results in persistent or significant disability/incapacity.
- Requires or prolongs in-patient hospitalization.

- Is a congenital anomaly/birth defect.
- Any other reason representing a significant hazard comparable to the criteria mentioned above.

Serious adverse reaction (SAR): an adverse event (expected or unexpected) that is both serious and, in the opinion of the reporting investigator, believed with reasonable probability to be due to one of the study treatments, based on the information provided.

Suspected unexpected serious adverse reaction (SUSAR): a serious adverse reaction, the nature or severity of which is not consistent with the applicable product information (e.g. Investigator's Brochure for an unapproved investigational product or summary of product characteristics for an approved product).

A central independent adjudication committee whose members are unaware of management allocation will adjudicate all suspected study outcomes during the study period.

Causality and expectedness

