The relationship of each adverse event to the trial intervention must be determined by a medically qualified individual according to the following definitions:

Related: The adverse event follows a reasonable temporal sequence from trial intervention. It cannot reasonably be attributed to any other cause.

Not Related: The adverse event is probably produced by the participant's clinical state or by other modes of therapy administered to the participant.

Procedures for recording AEs

All AEs occurring during the study observed by the investigator or reported by the participant, whether or not attributed to study intervention, will be recorded on the e-CRF.

The following information will be recorded: description, date of onset and end date, severity, assessment of relatedness to study intervention, other suspect drug or device and action taken. Follow-up information should be provided as necessary.

AEs considered related to the study intervention as judged by a medically qualified investigator or the sponsor will be followed until resolution or the event is considered stable. All related AEs that result in a participant's withdrawal from the study or are present at the end of the study, should be followed up until a satisfactory resolution occurs.

The relationship of AEs to the study intervention will be assessed by a medically qualified investigator. Any pregnancy occurring during the clinical study and the outcome of the pregnancy should be recorded and followed up for congenital abnormality or birth defect.

Reporting procedures for SAEs

All SAEs must be reported to the Steering Committee or designated organization within one working day of discovery or notification of the event.

The Steering Committee or designated organization will perform an initial check of the report, request any additional information. All SAE information must be recorded on an SAE forms and faxed to the Steering Committee or designated organization. Additional information received for a case (follow-up or corrections to the original case) need to be detailed on a new SAE form and faxed to the Steering Committee or designated organization.

It may be appropriate that some SAEs do not require immediate reporting, but this must be justified. Justification might be determined, for example, by admission to hospital, or prolongation of hospitalization, where this is to be expected in the underlying disease or condition.

Type and duration of follow-up of subjects after SAEs

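### The all-cause serious adverse event end point counts every death and COPD readmission of the efficacy composite, so serious non-bleeding harms are diluted unless they are also compared separately

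*Protocol*

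**What the plan says.** Protocol 1.3 and 2.7 and SAP 2.5.4 list SAEs within 90 days as a secondary safety end point ("Serious adverse events within 90 days after enrollment").

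The definition in Protocol 2.7, repeated in SAP 2.5.6, is broad. It reads "Serious adverse event: an event that fulfils one or more of the following criteria"; death is the first criterion, and another is "Requires or prolongs in-patient hospitalization". The underlying adverse event is one "which does not necessarily have to have a causal relationship with the study intervention".

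The efficacy composite covers the same 90 days: "The primary efficacy end point is the composite of death from any cause, non-fatal (recurrent) symptomatic VTE, or readmission for COPD exacerbation within 90 days".

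On analysis, the abbreviated protocol says under Secondary safety analysis: "All (dichotomized) end points will be analyzed by chi-square test on proportions", with a relative risk and 95% confidence interval. SAP 3.5.2 gives a relative risk and confidence interval for each end point.

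The only relaxation for hospital stays expected from the underlying disease is in Protocol 2.7: "It may be appropriate that some SAEs do not require immediate reporting, but this must be justified". It concerns the timing of reports, not what enters the end point, and Protocol section 6 still requires all SAEs to be collected. Relatedness is recorded for each event, but neither document plans an SAE analysis by relatedness or one without composite events.

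**The concern.** Two end points meant to answer different questions share most of their likely events. A COPD readmission counts against efficacy and, in the same patient, as an SAE. Once that patient is an SAE case, a contrast reaction, kidney injury or treatment complication leaves the patient's status unchanged.

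The abbreviated protocol names safety of the strategy as its secondary objective, although the objective lists in Protocol 1.3 and SAP 2.5.3 do not. Bleeding has two dedicated end points. Serious harm of any other kind, such as harm from CT or contrast, has only the SAE end point. At stake is whether its relative risk says anything about those harms or largely restates the efficacy result.

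**Working it through.** **1. The plan's own figures.** Protocol 2.10 and SAP 2.2 give 40% versus 30%, 80% power, 5% significance, 355 per arm, and 373 after allowing for 5% loss. The pooled two-sided formula gives [1.960·√(2·0.35·0.65) + 0.842·√(0.40·0.60 + 0.30·0.70)]² / 0.10² ≈ 356, against the stated 355. The inflation 355 × 1.05 = 372.75 rounds up to 373. So 40% and 30% are the rates the trial was sized on. At 40%, about 0.40 × 373 = 149 controls would have a composite event.

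**2. Overlap by definition.**
- Death from any cause: always an SAE.
- COPD readmission: always an SAE, because it is a hospitalization.
- Non-fatal symptomatic VTE: an SAE only if it meets a seriousness criterion.

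The overlapping rate may therefore be slightly below the composite rate.

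**3. Formula.** Let c be the composite rate, with all its events treated as SAEs, and q the rate of patients with any other SAE. The documents give no value for q, so it is assumed. If the two are independent, any-SAE = 1 − (1 − c)(1 − q).

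**4. Results** (control versus intervention):

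| Composite | Other SAEs (assumed) | Any SAE | RR, any SAE | RR, other SAEs |
|---|---|---|---|---|
| 40% vs 30% | 5% vs 10% | 43.0% vs 37.0% | 0.86 | 2.0 |
| 40% vs 30% | 10% vs 15% | 46.0% vs 40.5% | 0.88 | 1.5 |
| 40% vs 30% | 10% vs 20% | 46.0% vs 44.0% | 0.96 | 2.0 |
| 40% vs 35% | 5% vs 10% | 43.0% vs 41.5% | 0.97 | 2.0 |
| 40% vs 35% | 10% vs 20% | 46.0% vs 48.0% | 1.04 | 2.0 |
| 40% vs 40% | 5% vs 10% | 43.0% vs 46.0% | 1.07 | 2.0 |
| 40% vs 40% | 10% vs 15% | 46.0% vs 49.0% | 1.07 | 1.5 |

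First row: 1 − 0.60 × 0.95 = 0.430 and 1 − 0.70 × 0.90 = 0.370. Sixth row, intervention: 1 − 0.60 × 0.90 = 0.460.

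**5. Where the sign turns.** With 40% versus 30%, the any-SAE RR reaches 1 when q in the intervention arm equals 1 − 0.60(1 − q in controls)/0.70. That is 18.6% from a control rate of 5%, 22.9% from 10%, 31.4% from 20% and 40.0% from 30%.

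**6. Share of composite patients among control SAE patients.** This is 0.40 divided by any-SAE: 93%, 87%, 77% and 69% for q of 5%, 10%, 20% and 30%.

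**7. Power at 355 per arm, 5% versus 10% other SAEs.** Compared on their own, the other SAEs reach significance with probability about 72%. Through the all-SAE end point with no efficacy benefit, it is about 12%. With the planned benefit, there is about a 37% chance of a significant all-SAE difference in favour of the strategy.

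**8. Independence.** For 5% versus 10%, the extremes are other SAEs occurring only in composite patients, or only in patients without a composite event.
- 40% versus 30%: RR 30/40 = 0.75 to 40/45 = 0.89.
- 40% versus 40%: RR 40/40 = 1.00 to 50/45 = 1.11.

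The pattern holds throughout.

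**The case against.** The best defence is that all-cause SAE reporting is a legitimate choice. It needs no causality judgement, which is useful in an open-label trial, and it loses no fatal event. That stands, and the end point should not be removed or replaced.

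A reader might infer that the plan conceals the strategy's harms. The documents do not support this.
- Major bleeding, the primary safety end point, and clinically relevant non-major bleeding are analysed separately. They share nothing with the composite except fatal bleeding.
- Protocol 2.7 records every adverse event individually with severity and relatedness, SAEs alert the data safety monitoring board, and Protocol 4.4 gives that board periodic safety reports.
- SAP 3.5.2 says secondary end points are unadjusted for multiplicity and should not be used to infer effects of the intervention.

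The limit on inference restrains formal claims. The relative risk and interval will still be published, and a value below 1 can reassure wrongly.

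The assumed rates can also be challenged. Other SAEs include every non-COPD hospitalization, so the background may exceed 5%. The 40% rests on readmission without a stated cause, whereas the end point is now COPD readmission, so the overlap may be smaller. An excess of 5 points over the whole intervention arm (0.05 × 373 ≈ 19 patients) is large, since only D-dimer-positive patients have CT and only confirmed PE leads to anticoagulation. These points reduce the size of the effect. They do not remove the overlap.

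**Conclusion.** The overlap is certain from the definitions, and no planned analysis separates the two kinds of event. Its size is conditional. If the 40% versus 30% benefit is real, the all-SAE RR can fall below 1 while other SAEs rise: 0.86 when they double from an assumed 5% to 10%. A reader might infer that the strategy would look safer whatever the truth. It would not: with no efficacy benefit the direction is right, and the fault is dilution, RR 1.07 in place of 2.0.

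The figures rest on assumed rates of other SAEs, on independence (range in step 8), and on nearly all composite events being serious. The weakness is confined to serious non-bleeding harm. The primary analysis and both bleeding end points are unaffected. It is a gap worth closing because closing it is cheap, not an error that undermines the trial.

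**What to change.** In SAP 3.5.2, keep the all-SAE end point as it is and prespecify beside it a per-patient comparison, with relative risk and 95% confidence interval, of SAEs other than adjudicated COPD readmission, adjudicated non-fatal VTE and death. Specify that:
- a patient's other SAEs count even when that patient also had a composite event;
- a death adjudicated as due to bleeding, or judged related to the intervention, stays in the count;
- SAEs are also tabulated by arm and recorded relatedness.

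The data exist. The e-CRF holds the primary causes of death and rehospitalization (Protocol 3.4), Protocol 4.3 adjudicates outcomes and classifies deaths as due to PE, COPD, bleeding or another cause, and Protocol 2.7 records relatedness. There is no adjudication category for procedure-related death, so the relatedness judgement has to identify those deaths.

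The cost is one derived variable, one table and less precision. For 373 per arm and 5% versus 10%, the standard error of the log relative risk is √(1/18.65 + 1/37.3 − 2/373) ≈ 0.27. For all SAEs at 43% versus 37% it is √(1/160.4 + 1/138.0 − 2/373) ≈ 0.09. The wider interval is the price of measuring the right quantity.
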